# **Screening Cognitive Battery:**

Participants will undergo a cognitive assessment at screening using the Uniform Data Set (UDS) version 3 test battery. Objective tests of cognitive function will include the following: global cognitive function (MOCA, MMSE), CDR, premorbid cognitive function (AMNART, Rey Auditory Verbal Learning Test), memory (Craft Story), visual memory (Benson Complex Figure), attention/concentration (forward and backward Number Span, Trails A/B), and language/verbal fluency (Verbal/Category Fluency, Multilingual Naming Test).

## **Diet Cognitive Battery**

Once participants have been enrolled in the study they will complete another cognitive battery that will measure the effect of diet on cognition. The Diet Cognitive Battery will consist of the Preclinical Alzheimer Cognitive Composite (PACC), CogState computerized test battery, the Alzheimer's Disease Assessment Scale – cognitive subscale (ADAS-cog) version 12, the Alzheimer's Disease Cooperative Study – Activities of Daily Living Scale (ADCS-ADL), and the Geriatric Depression Scale (GDS). The major components of each battery are outlined below:

- **1. PACC** (primary cognitive endpoint):
  - i. Free and Cued Selective Reminding Test Total Recall: The FCSRT measures verbal memory through controlled learning of a list 16 words that are introduced to participants by both visual and auditory presentations. Once the participant has learned the list they immediately recall each item. Then after a

- delay of 20 minutes participants are asked to recall the items over three trials. The total score is the sum of free and cued words recalled over all three trials.
- ii. Logical Memory IIa Delayed Paragraph Recall: Participants will be read a story divided into 'bits' of information containing main content words. The participant recalls the story immediately, then again after a 20 minute delay. The total number of 'bits' remembered after the delay will be calculated as the delayed recall score.
- iii. **Digit Symbol Substitution Test:** The participant will be introduced to a sheet of paper with a key that matches numbers 1-9 with an unfamiliar symbol. The participant must work as fast as possible for 90 seconds to match a random list of numbers 1-9 with their associated symbol.
- iv. **MMSE Total Score:** The MMSE is a questionnaire read to participants and tests multiple areas of cognition. The total number of questions right indicate general cognitive ability with higher numbers representing higher cognitive function.
- v. **Category Fluency:** Participants will be given a category then asked to verbally generate nouns that belong to that category. The total number of correct items generated in 60 seconds will be summed.

# 2. CogState Computerized Test Battery:

- i. Tests of Learning and memory
  - i. Object Pattern Separation Task (OPST), target pictures of common objects are presented along with highly similar "lures" and participants must identify targets;
  - **ii.** One Card Learning (OCL) Test, a playing card is presented and the participant must decide whether he/she has been shown that card before. The arcsine proportion correct is calculated
- ii. Tests of psychomotor speed:
  - i. Detection Test (DT), as soon as a playing card is presented, the participant must press the "Yes" key;
  - In the Identification Test (IDT), the participant must decide whether the card presented is red. Number correct and/or mean correct response time in log (msec) are recorded.
- **3. ADAS-Cog 12:** The ADAS-Cog 12 will also be administered to provide data to inform future trial design. The ADAS-Cog 12 is a psychometric instrument that evaluates memory, attention, reasoning, language, orientation, and praxis. A higher score indicates more impairment. Scores from the original portion of the test range from 0 (best) to 70 (worse) and then number of items not recalled ranging from 0-10 is added for a maximum score of 80. A positive change indicates cognitive worsening. The ADAS-Cog12 version will be used in the current study, which includes Delayed Word Recall a measure of episodic memory.
- 4. ADCS-ADL: The Alzheimer's Disease Cooperative Study Activities of Daily Living Scale (ADCS-ADL) is an activities of daily living questionnaire aimed at detecting functional decline in people with Mild Cognitive Impairment (MCI). It was adapted from an inventory developed by the ADCS to assess functional performance in participants with Alzheimer's disease. In a structured interview format, informants are queried as to whether participants attempted each item in the inventory during the prior 4 weeks and their level of performance. The ADCS-ADL-MCI scale discriminates well between normal controls and patients with mild AD or MCI. It has good test-retest reliability. The questions focus predominantly on instrumental activities of daily living scales (e.g. shopping, preparing meals, using household appliances, keeping appointments, reading).

- 5. Geriatric Depression Scale: The Geriatric Depression Scale (GDS) is a well-validated self-report questionnaire used frequently in clinical and research settings to assess mood in older adults. This questionnaire includes 15 questions and takes about 5-7 minutes to complete. The GDS will be used as a part of the screening cognitive battery to determine whether participants should be excluded due to a significant presence of depressive symptoms.
- 6. **Neuropsychiatric Inventory Questionnaire:** The neuropsychiatric inventory questionnaire (NPI-Q) is widely used to assess the presence of mood disorders in geriatric populations. The NPI-Q measures 12 symptom categories and is scored on a scale of 0-36. An informant or caregiver for the participant must answer each question by indicating Yes or No for the presence of a symptom and when present they rate the severity on a scale of 1-3.

# **Imaging Procedures**

Imaging for this study will include PET, MRI and a DEXA scan. The protocols for each are described below.

# Positron Emission Tomography (PET)

Dual Tracer PET scans (dtPET): A separate consent form for dual tracer PET administration and data collection will be administered to all participants (IRB# 00033365). 11C-AcAc will be synthesized as described previously. 54, 55 PET scans will be performed on a GE Discovery PET/CT scanner with an isotropic voxel size of 2 mm^3, field-of-view of 25 cm, and axial field of 18 cm. Imaging with C-AcAc will be conducted first with acquisition frames of 12x10 sec, 8x30 sec, and 1x4 min (total scan 10 min), followed by a 50-min wash-out. FDG imaging is then conducted, using the time frames 12x10 sec. 8x30 sec, 6x4 min, and 3x10 min (total scan 60 min). Indwelling catheters will be placed in forearm veins for the injection of 5-10 mci of tracer. Blood samples will be obtained at 3, 6, and 8 min after the C-AcAc infusion and at 3, 8, 16, 24, 35 and 55 min after FDG infusion. Radioactivity in plasma samples is counted in a gamma counter cross-calibrated with the PET scanner. PET images are preprocessed and co-registered to each participant's MR using a cross-modality 3D image fusion tool in PMOD 3.5. Coregistered PET images are corrected for PVE with the modified Müller-Gartner method. Using the PMOD 3.5 pixel-wise kinetic modeling tool, parametric images of CMRq and CMRa will be produced for each participant. CMR quantification requires an arterial input function, determined by tracing regions of interest (ROIs) on the internal carotid arteries with the aid of co-registered MR images as previously validated. The calculated activity within the ROI will be corrected using the radioactivity of the plasma samples obtained during image acquisition. The lumped constant will be set to 0.89 for the CMRg calculation, and to 1.0 for the CMRa calculation. CMRg and CMRa will be expressed as mmol/100 g/min using the graphical Patlak model. CMRa will be corrected for loss of 5.9% of the dose of C-AcAc that is catabolized to CO2.  Key outcomes for analysis will be global C-acetoacetate uptake and the PALZ PMOD index for 18F-FDG PET. 61

**β-Amyloid PET Imaging (amyPET):** All study participants will receive an amyloid PET scan. A separate consent form for amyloid PET administration and data collection will be administered to all participants (IRB# 00027675). Amyloid PET data will be used to confirm Alzheimer's pathology and will be added to the PET imaging repository of the ADCC. Participants will be injected with an iv bolus of up to 15mCi (370 MBq) (+/- 10%) of C-Pittsburgh compound B (PiB, over 5-10 seconds), followed by a 40 min uptake period (+/- 10%). Brain emission images will be acquired continuously for a 30 min to quantify amyloid uptake in MRI-defined regions, acquired in six 5-minute frames. Participants will be contacted 24-72 hours after injection with C-PiB to inquire if any adverse events occurred within 24 hours of injection.

Aβ deposition in the brain will be quantified by C-PiB uptake using standardized uptake volume ratio (SUVR) of 5 primary cortical areas (anterior cingulate; posterior cingulate/precuneus; frontal, lateral temporal and parietal cortex) relative to cerebellar gray matter. The unweighted average of these 5 regions will be used to determine amyloid positivity. Averages<1.35 will be considered amyloid negative.

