## ETHICS/PROTECTION OF HUMAN SUBJECTS

## **Informed Consent**

Signed informed consent will be obtained from each participant. Once participants have been identified for potential inclusion into the study, a study team member will explain the nature of the study and the study procedures by reviewing the material presented on the consent form. Potential participants who express interest in the study will then be asked to meet with the study coordinator in person, at which time the consent form will be reviewed again, and questions and concerns related to the study will be solicited. Once informed consent has been obtained, potential participants will undergo clinical evaluation to ensure they meet the inclusionary criteria for the study. To avoid coercion, the study team will stress, both in the initial telephone contact and in follow-up appointments: 1) that all research participation is voluntary, 2) that participants may withdraw at any time, 3) the decision to participate or not participate will not affect the participants' medical care or any benefits to which the participant is entitled, and 4) encourage questions about the study.

[name], the study coordinator, and project collaborators will develop the consent forms. The consent form will include all of the required elements of informed consent required by the FDA. The principles of informed consent in the current edition of the Declaration of Helsinki will be implemented.

Information will be given in both oral and written form. Participants, their relatives, guardians, or authorized representatives and informants will be given ample opportunity to inquire about the details of the study. All investigators will attend a training meeting prior to the start of participant recruitment. Informed consent will be documented by the use of a written consent form approved by the IRB and signed by the participant and/or a legally authorized representative.

Potential participants for this trial may be recruited from other ongoing studies in affiliation with the ADCC; data from blood, CSF, cognitive testing, and imaging measures may be utilized for this trial as long as a participant is enrolled within 6 months of the start of the diet intervention.

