All participants will be rigorously screened by MRI personnel to be certain that they do not have any medical contraindications for MRI, which include metallic foreign bodies in the brain or eye or cardiac pacemaker. This safety screening is part of routine clinical practice at MRI centers and is performed before any participant is permitted to enter the scanning room. There is a slight risk of anxiety due to claustrophobia. Any participant who experiences anxiety when placed into the MR scanner will be removed from the scanner, offered reassurance by the MRI technician doing the scan, and offered the option of continuing or terminating the scan. If the participant decides that the anxiety associated with MRI is uncomfortable for them and they wish to terminate the scan, then the examination will be ended at that time. There will be no attempt to coerce participants to complete exams that they are uncomfortable with. Participants uncomfortable with MRI scans should preferably not be included in this study. Use of anxiolytic agents for completion of MRI scans is discouraged, but allowed at the discretion of study clinicians.

**Risks Associated with PET imaging:** PET imaging scans involve exposure to radiation. The amount of radiation exposure is considered low and comparable to everyday risks. For the three PET scans participants will receive about 3 Rem of exposure to radiation. This is the below the annual dose limit per patient of 5 Rem.

**Risks Associated with DEXA:** DEXA scans involve exposure to radiation. Although it can vary from person to person, whole-body radiation exposure from the two DEXA scans will be less than 6 mRem. The average annual exposure a person in the United States receives from natural background radiation is about 300 mRem. The risk of harm from this amount of radiation is low and no harmful health effects

are expected; however, risk of harmful effects may increase if the participant is exposed to more procedures that involve radiation within a short period of time.

**Risks Associated with Blood Draw:** Transient discomfort and bruising may occur when plasma is drawn, and there is a small risk of infection with any blood draw. In our experience, the discomfort associated with blood draws is usually minimal; every effort will be made to minimize any discomfort.

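### The 11C-PiB activity limit is given as 15 mCi and as 370 MBq, but 15 mCi is 555 MBq; the two limits differ by a factor of 1.5

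*Combined protocol and SAP*

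**What the plan says.** The subsection on β-amyloid PET (amyPET), under Positron Emission Tomography in the imaging procedures, sets the 11C-PiB activity for a scan that all participants are to have: "Participants will be injected with an iv bolus of up to 15mCi (370 MBq) (+/- 10" (the percent sign and closing bracket follow). The MBq value stands in parentheses as the equivalent of the mCi value. The protocol gives the PiB activity nowhere else.

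Two other places provide context:

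- The dual tracer PET text gives an activity for different tracers: "Indwelling catheters will be placed in forearm veins for the injection of 5-10 mci of tracer".
- The paragraph on PET risks, under Potential Risks and Protections Against Risks, gives a combined exposure: "For the three PET scans participants will receive about 3 Rem of exposure to radiation". It compares this with an annual limit: "This is the below the annual dose limit per patient of 5 Rem". It does not break the total down by tracer or state the activities behind it.

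**The concern.** A parenthesis after a quantity normally restates it in another unit. Here the two numbers describe different activities, and the sentence sets an upper limit on a radioactive injection. Someone working in mCi would allow half as much again as someone working in MBq. A monitor checking an injection record against this text could not say which limit governs.

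The exposure statement is also affected. The protocol reassures the reader by comparing about 3 Rem with 5 Rem, but the 3 Rem could rest on either PiB activity. If it rests on the smaller one, it understates the exposure at the 15 mCi limit.

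**Working it through.** **Inputs.** From the amyPET subsection: 15 mCi, 370 MBq, tolerance ±10%. From the PET risk paragraph: about 3 Rem for three PET scans, limit 5 Rem. From the DEXA risk paragraph: less than 6 mRem for two scans. By definition of the units, 1 Ci = 3.7 × 10¹⁰ Bq, so 1 mCi = 37 MBq.

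**Conversion.** The plan's pairing cannot be reproduced in either direction:

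- 15 mCi × 37 = 555 MBq, not 370 MBq.
- 370 MBq ÷ 37 = 10 mCi, not 15 mCi.
- Ratio 555 ÷ 370 = 1.5; difference 555 − 370 = 185 MBq, or 5 mCi.

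**Tolerance.**

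| Figure taken as intended | −10% | Nominal | +10% |
|---|---|---|---|
| 370 MBq (10 mCi) | 333 MBq | 370 MBq | 407 MBq |
| 15 mCi (555 MBq) | 499.5 MBq | 555 MBq | 610.5 MBq |

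The bands do not overlap (407 is below 499.5), so neither rounding nor the tolerance reconciles the figures.

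**Disputed range.** Because the text sets an upper limit, anything up to 407 MBq complies with both figures. From above 407 MBq to 555 MBq (610.5 MBq with tolerance), an injection complies with the mCi figure and exceeds the MBq figure.

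**Exposure.** The documents do not give the PiB share of the 3 Rem; call it *s*. Assume that dose is proportional to activity and that the 3 Rem was computed with PiB at 370 MBq. At the 15 mCi limit:

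- nominal total = 3 × (1 + 0.5*s*);
- with +10%, since 1.5 × 1.1 = 1.65, total = 3 × (1 + 0.65*s*).

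| Assumed share *s* | At 15 mCi | At 15 mCi + 10% |
|---|---|---|
| 1/3 (illustration only) | 3.5 Rem | 3.65 Rem |
| 1 (outer bound, not attainable) | 4.5 Rem | 4.95 Rem |

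The second row is not attainable because the 3 Rem also covers the dual tracer scans. Even there, adding DEXA gives 4.95 + 0.006 = 4.956 Rem, below 5 Rem. If the 3 Rem was instead computed at 555 MBq, it already covers the larger limit apart from the tolerance.

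**Extent.** With 120 participants and one amyloid scan each, at most 120 injections are affected. The number may be smaller, because the Informed Consent section lets "data from blood, CSF, cognitive testing, and imaging measures may be utilized for this trial" come from earlier studies.

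**The case against.** The best case for leaving the text alone has four parts.

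- **Another protocol may set the activity.** Amyloid PET has its own consent form under a separate IRB number, so staff may take the activity from that protocol. This lowers the practical risk. However, the present text does not say that the other document controls dosing, and it states a limit of its own.
- **The wording sets a maximum.** Any injection at or below 370 MBq satisfies both figures, and nothing shows that higher activities are planned. This is correct, and it confines the problem to the range above 407 MBq.
- **The exposure range is loosely bounded.** PiB cannot supply all of the 3 Rem, because each of the two dual tracer sessions injects two other tracers. Nor do the documents support one third as a minimum share. Both points stand. On the stated assumptions the nominal total lies somewhere above 3 and below 4.5 Rem. The calculation shows only that the 3 Rem figure needs checking; it shows no harm.
- **The results are unaffected.** The primary endpoint is CSF Aβ42, and amyloid positivity rests on an SUVR, a ratio of regions within one scan. This is also correct, and no effect on the results is claimed.

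None of this makes the two figures agree. The dual tracer range of 5–10 mCi cannot settle the matter, because it concerns other tracers.

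**Conclusion.** The inconsistency is certain, because it rests only on the definition of the units. The two stated limits differ by 185 MBq, a factor of 1.5. Injections above 407 MBq and up to 555 MBq (610.5 MBq with tolerance) cannot be classified as compliant or not from this protocol. The documents do not show which figure is intended, and none is preferred here.

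The effect on exposure is conditional. It depends on the activity behind the 3 Rem, on the unstated PiB share and on dose being proportional to activity. Under the least favourable assumptions the total stays below 5 Rem. The point should be fixed because it concerns a radioactivity limit in a procedure planned for every participant, not because harm or bias has been shown.

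**What to change.** In the amyPET subsection, state one activity with its correct conversion: either 15 mCi (555 MBq) or 10 mCi (370 MBq). Take it from the activity approved under the separate amyloid PET protocol. Then confirm that the total of about 3 Rem in the PET risk paragraph was computed with that activity, and restate the total if it was not.

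The cost is a one-line protocol correction and one check of the dosimetry calculation. The design, sample size and analysis do not change.

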# Magnetic Resonance Imaging (MRI)

Magnetic resonance images will be acquired on a 3 Tesla Siemens MAGNETOM Skyra scanner with a high-resolution 32-channel head coil (Erlangen, Germany) located in the MRI building at the Wake Forest Baptist Medical Center. The MRI session will last 45 -60 minutes and include 6 unique sequences that assess multiple levels of brain structure, connectivity, function, and cerebral blood flow. The acquisition parameters of each sequence are detailed below:

# **Image Acquisition Parameters:**

- Resting-State BOLD: For the resting state paradigm the subject will be instructed to rest quietly with eyes open. High resolution BOLD images will be acquired using the following parameters, time of recoil (TR) = 868 ms; time of echo (TE) = 30.6 ms, flip angle (FA) = 52°; field of view (FoV) = 208 mm, and a total of 72 slices with a voxel size of 2.0 mm^3. Slices will be collected in an interleaved series and oriented in the transverse plane.
- Anatomical MPRAGE: Anatomical T1 images will be obtained using a 3D volumetric MPRAGE sequence. Acquisition parameters are as follows; TR = 2300 ms; TE = 2.98 ms; TI = 900 ms, FA = 9°, FoV = 256 mm and a total of 192 slices with a voxel size of 1.0 mm^3. Slices will be collected in an ascending order and oriented in the transverse plane.
- T2 FLAIR: The T2 FLAIR paradigm will measure brain structure under different contrast of brain fluids compared to the T1 image. T2 FLAIR images will be acquired using the following parameters; TR = 5000 ms; TE = 383 ms; TI = 1800 ms, FoV = 256 mm and a total of 192 slices with a voxel size of 1.0 mm^3. Slices will be collected in an interleaved series and oriented in the transverse plane.
- Neurite Orientation Dispersion and Density Imaging (NODDI)- DTI: The NODDI-DTI sequence will measure brain white matter structure. Acquisition parameters are as follows, TR=3500 ms; TE=106 ms; FA=90° with multiple diffusion weighting shells (b=1000, 2500, and 4000 s/mm2 with 15 b=0) that provides orientation dispersion index, intra-cellular volume fraction as well as the conventional diffusion tensor maps. Diffusion parameters include a 30-direction scan with a 2 mm isotropic spatial resolution. Slices will be collected in an interleaved series and oriented in the transverse plane.
- Susceptibility weighted imaging quantitative susceptibility mapping (SWI-QSM): The SWI-QSM sequence is an enhanced image contrast to measure cerebral venous architecture. The acquisition parameters are as follows, TR=51 ms; multiple TE 1-6 = 9.8 ms, 16.6 ms, 23.5 ms, 30.4 ms, 37.3 ms, 44.2 ms; FA=20°, FoV = 240 mm and a total of 64 slices with a voxel size of 0.6x0.6x2.0mm. Slices will be collected in an interleaved series and oriented in the transverse plane.
- Pseudo Continuous Arterial Spin Labeling (PCASL): Whole-brain resting baseline cerebral blood flow (CBF) will be acquired with a pseudo-continuous ASL (PCASL) sequence.
   Participants will be asked to sit still with their eyes open then hold their breath during a second brief pcASL acquisition. The acquisition parameters are as follows, TR = 4000 ms, TE = 11 ms,

TI = 3000 ms, FA =  $90^{\circ}$ , FOV = 240 mm, with a total of 36, 4 mm axial slices with a voxel size of 3.0x3.0x4.0mm. Slices will be collected in an ascending series and oriented in the transverse plane. Quantitative perfusion maps (mL/100 gm tissue/min) for each voxel are computed as previously described.

**Lumbar Puncture (LP) Procedure and CSF Assays:** All participants will undergo LP before 11 a.m. after fasting for ≥12 hours. Using a 22-gauge Sprotte needle to drip, up to 25ml of CSF will be withdrawn into sterile polypropylene tubes. CSF will be transferred in 0.2 ml aliquots into pre-chilled polypropylene tubes, frozen immediately on dry ice, and stored at -80°C until assay. CSF will be analyzed for AD biomarkers (Aβ42, tau, p-tau) using the AlzBio3 multiplex assay (FujiRebio Europe). Participants will be fed following the LP. The participant will rest in the recumbent position for 30 minutes post-LP. A recent Cochrane Review did not find that bed rest or IV fluid administration reduced the risk of post-LP headache. Study participants or authorized caregivers will be contacted by phone within 24 hours of the LP to inquire about any adverse events. Participants will sign a repository-consent for storage of samples at the time of study consent.

**Redox Proteomic/Lipidomic Assays:** For the determination of free fatty acids (FFAs), 200 μl of CSF will be extracted using chloroform/methanol according to a modified method of Bligh and Dyer,  in which the aqueous phase is adjusted to pH 3 or lower with HCl prior to extraction. Pentadecanoic and heneicosanoic acids (Nu Chek Prep) will be added to each sample prior to extraction as internal standards. The lipid extracts will be evaporated under a stream of argon, and the FFAs isolated by the solid phase extraction method of Kaluzny et al.  using 500 mg amino-SPE columns (Thermo Scientific). FFAs will then be derivatized to their fatty acid methyl esters by treating with 1 ml of 14% BF3 in methanol (Sigma-Aldrich) under Argon, and heating to 100°C for 10 minutes. After cooling, the samples will be treated with 1 ml of hexane and 4 ml of saturated, aqueous NaCl. The hexane phase will be transferred to a sample vial, and 1 μl analyzed on a TSQ Quantum XLS GC/MS/MS interfaced to a Trace GC Ultra (Thermo Electron Corp.), automated by a TriPlus auto-sampler. Separation will be accomplished using a 30 m × 0.25 mm diameter DB-WAX ETR column (Agilent Technologies) with a 0.25-μm coating as reported previously.  Sphingolipids and ceramides will be analyzed using published methods. 

**DEXA Procedure:** Participants will receive body fat assessments as part of the Pre-Diet and Post-Diet Study Visits. Total fat mass, fat-free mass, and their relative distributions will be determined using dual energy x-ray absorptiometry (DEXA) measurements. For this test, participants cannot have removable metal objects on their body, such as snaps, belts, underwire bras, and jewelry. This test will last about 20-30 minutes.

